Pathways to cardiovascular disease prevention and impact of specialty referral in under-represented racial/ethnic minorities with HIV.

ClinicalTrials.gov ID NCT04025125

Protocol Title	Pathways to cardiovascular disease prevention and impact of specialty referral in underrepresented racial/ethnic minorities with HIV. (DCRI Central and Statistical Coordinating Center)		
Protocol Short Title	Pathways to CVD Prevention (DCRI Central and Statistical Coordinating Center)		
Protocol identifying number	Pro00101104		
Principal Investigator	[name], MPH		
	Duke University Health System		
	Duke Clinical Research Institute		
Funded by	NIH		
Protocol version identifier	v.4.0		
Date of last version of protocol	27 November 2024		
Research objectives	
 
To identify factors associated with cardiology referral in under-represented racial and ethnic minority (URM) populations with HIV and elevated cardiovascular risk
 
To evaluate the association between cardiology referral and CVD outcomes in under-represented racial and ethnic populations with HIV and elevated cardiovascular risk
 
To evaluate the association between
 
		
	cardiology referral and guideline-directed CVD prevention measures in URM populations with HIV and elevated CVD risk  3. To identify facilitators and barriers to optimal CVD prevention using semistructured interviews		

16 LITERATURE CITED	

## 1. List of Abbreviations

Antiretroviral therapy	
Common Data Model	
Clinical Research Network	
Cardiovascular Disease	
Case Western Reserve University	
Duke Clinical Research Institute	
Duke University Health System	
Distributed Research Network Operations Center	
Electronic Health Record	
Human Immunodeficiency Virus	
Medical University of South Carolina	
National Death Index	
National Provider Identifier	
The National Patient Centered Clinical Research Network	
People Living with HIV	
Protected Health Information	
Research Assistant	
Under-Represented Racial and Ethnic Minority	
Vanderbilt University Medical Center	
Wake Forest University Health Sciences	

## 3 Amendments and Updates

a. Update cover page on November 27, 2024 for clinicaltrials.gov information.

## 4 Purpose of the study

- 1. To identify factors associated with cardiology referral in under-represented racial and ethnic minority (URM) populations with HIV and elevated cardiovascular risk
- 2. To evaluate the association between cardiology referral and CVD outcomes in under-represented racial and ethnic populations with HIV and elevated cardiovascular risk
  - a. To evaluate the association between cardiology referral and guideline-based CVD prevention measures in URM populations with HIV and elevated CVD risk
- 3. To identify facilitators and barriers to optimal CVD prevention

#### Hypotheses to be tested:

- 1. We hypothesize that patient- (e.g., health insurance) and provider-level (e.g., patient-provider race discordance) factors are associated with cardiology referral in URM people living with HIV (PLWH) at elevated CVD risk. The primary outcome measure is visit with a cardiologist after meeting criteria for elevated CVD risk.
- 2. We hypothesize that URM PLWH who are seen by a cardiologist will have better CVD outcomes compared to those without referral. Primary outcomes are blood pressure and lipid control, and secondary outcomes are myocardial infarction, stroke, death and cardiovascular death both individually and as a composite, as a function of whether an individual at elevated CVD risk was seen by a cardiologist prior to first event.
  - a. We hypothesize that guideline-directed care including tobacco cessation counseling, cardiac testing, blood pressure and cholesterol medication management, glycemic control and appropriate use of statins mediate the relationship between cardiology referral and CVD outcomes.
- 3. Aim 3 is not driven by a pre-specified hypothesis.

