Then, DCRI will take the query data that the sites provide to identify and further stratify data for potential cohort of patients, based on additional clinical characteristics. At the earliest clinical contact within look back period, we will identify HIV status according to ICD9/10 codes and prescription of ART. We will include individuals >18 years of age and < 99 years of age, plus will ascertain time-updated data for the following potential characteristics:

hemoglobin, creatinine (or glomerular filtration rate), age, sex, race, ethnicity, insurance status, total cholesterol, HDL cholesterol, LDL cholesterol, systolic blood pressure, prescription of anti-hypertensive medications, family history of coronary artery disease, presence of diabetes, previous diagnosis of any acute myocardial infarction, hospitalization for heart failure, acute coronary syndromes, stable or unstable angina, arterial revascularization, stroke, transient ischemic attack and peripheral arterial disease presumed to be of atherosclerotic origin determined by ICD9/10 codes. Behavioral factors are smoking status, number of clinic visits per year, length of time between clinic visits and missed appointments with specialist after referral. Data will also be ascertained on HIV viral load, CD4 count, prescription of any ART and length of time on all medications. This list captures the majority of the data related to our scientific aims and will be modified as the availability of these data are discovered.

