## 12 Data analysis & statistical considerations

#### 12.1 Analysis Plan for Aim 1

For this aim, the primary outcome variable is referral to a cardiology specialist within 6 months of baseline. This will be measured as a binary variable, with 'yes' defined if there is documented evidence that a referral is made within 6 months of becoming eligible by CVD risk score and kept within 3 months of referral, and 'no' otherwise. We will also determine the time from baseline to cardiology referral and the time until the first visit with the cardiology specialist.

We will consider a number of patient and provider factors evaluated at baseline that are potentially associated with referral to a cardiology specialist. Patient factors will include demographic factors (age, sex, race, ethnicity), level of ASCVD risk, Charlson comorbidity index, SES (e.g.; 5 digit zip code, health insurance ([yes/no]), type of health insurance (Medicare, Medicaid, private, Ryan White, etc.), and history of keeping appointments during 2 years prior to baseline. Provider factors will include primary management strategy (coprimary management defined as having both an HIV doctor and Primary Care Practitioner vs. HIV provider as primary care), and years of practice since training. Cardiologist availability will be a site-determined variable. Based on prior literature, we are specifically considering sex as a biological variable that may be related to specialty referral. 

Baseline characteristics of the cohort will be summarized overall and by referral status. We will include the patient and provider factors described above, as well as vital signs (including weight, body mass index and blood pressure), laboratory measures (particularly total and HDL cholesterol, CD4 cell count, HIV viral load), and relevant medications (ART and cardiovascular medications). We will document the patterns of HIV related CVD comorbidity in the study population, as the funding opportunity announcement specified.

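### Aim 1 sets out to study referral, but its primary outcome is defined in three ways and the scored version cannot separate referral from attendance

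*Combined protocol and SAP*

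**What the plan says.** Section 4 states the aim as "To identify factors associated with cardiology referral in under-represented racial and ethnic minority (URM) populations with HIV and elevated cardiovascular risk". The hypotheses in the same section give the outcome for it: "The primary outcome measure is visit with a cardiologist after meeting criteria for elevated CVD risk". That sentence sets no window and does not require a referral.

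Section 12.1 opens with a different outcome: "the primary outcome variable is referral to a cardiology specialist within 6 months of baseline". Its scoring rule then requires documented evidence that "referral is made within 6 months of becoming eligible by CVD risk score and kept within 3 months of referral, and 'no' otherwise". Attendance is therefore part of the scored variable.

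The plan also collects information on the separate steps. Section 12.1 adds: "We will also determine the time from baseline to cardiology referral and the time until the first visit with the cardiology specialist". Section 8.1 lists "missed appointments with specialist after referral" among the data to be ascertained. The candidate factors in Section 12.1 include "history of keeping appointments during 2 years prior to baseline". The regressions, however, are specified only for cardiology referral as a single binary outcome. The one sensitivity analysis that changes that outcome lengthens the referral window from 6 to 12 months. Section 12.2 takes the Aim 1 outcome as the Aim 2 exposure and starts follow-up when the referred patient kept the appointment.

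**The concern.** There are two separate problems.

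The first is definitional. A primary outcome with three versions leaves the analyst to choose among them, and they disagree on identifiable groups of patients.

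The second concerns interpretation. Making a referral is largely the provider's act, while keeping it depends on the patient and on access. Under the scoring rule, a patient who was referred and did not attend is coded the same as a patient nobody referred. A factor that acts only on attendance would then be reported as a factor associated with referral. Insurance and past appointment keeping are obvious candidates. Section 5 says that knowing how these patients access cardiology referrals should help in designing an intervention. Prompting providers to refer and helping patients attend are different interventions, and the composite alone cannot say which one a factor points to.

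**Working it through.** **Step 1: the three definitions side by side.**

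| Patient | Section 4 | 12.1 opening sentence | 12.1 scoring rule |
|---|---|---|---|
| Referred by 6 months, seen within 3 months of referral | yes | yes | yes |
| Referred by 6 months, never attends | no | yes | no |
| Referred by 6 months, seen more than 3 months after referral | yes | yes | no |
| Referred in month 8, then seen | yes | no | no |
| Seen with no documented referral | yes | no | no |
| Neither referred nor seen | no | no | no |

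Section 4 and the scoring rule disagree on visits without a documented referral and on visits outside the windows. They agree on the referred patient who never attends. On that patient the disagreement lies within Section 12.1, between its opening sentence and its rule.

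**Step 2: the plan's own power figures.** Inputs from Section 12.1.1: N = 1,200 to 1,500, 20-25% referred, binary factor with prevalence 0.33. The 0.05 two-sided level is in Section 12.1. The two group rates p0 and p1 are solved so that 0.67·p0 + 0.33·p1 equals the overall rate and their odds ratio equals the target. A pooled two-proportion test is then applied.

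- N = 1,200, 20%, OR 1.6: p0 = 0.1742, p1 = 0.2524, power 88.0%. The plan says at least 80%.
- N = 1,500, 20%, OR 1.5: p0 = 0.1778, p1 = 0.2450, power 85.5%; at 25% it is 90.2%. The plan says above 85%.

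The stated power is reproduced.

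**Step 3: a factor with no effect on referral.** Let r be the share referred, equal in both groups, and a the share of referrals kept. The composite rate is p = r·a, and OR = [p1/(1−p1)] / [p0/(1−p0)]. Take r = 0.25, the top of the plan's range. The attendance values are assumptions, because the documents give none. With a = 80% in the comparison group, p0 = 0.25 × 0.80 = 0.20 and the odds are 0.25.

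| Attendance in the other group | p1 | Odds | Composite OR |
|---|---|---|---|
| 75% | 0.1875 | 0.2308 | 0.92 |
| 70% | 0.1750 | 0.2121 | 0.85 |
| 60% | 0.1500 | 0.1765 | 0.71 |
| 50% | 0.1250 | 0.1429 | 0.57 |

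With r = 0.20 the last two become 0.72 and 0.58. The effect size in the power statement, inverted, is 1/1.6 = 0.625. Reaching it needs odds of 0.625 × 0.25 = 0.156, so p1 = 0.135 and attendance of 0.135/0.25 = 54%, a gap of 26 percentage points.

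**Step 4: a factor with a true referral OR of 1.6** (prevalence 0.33, 20-25% referred).

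- Equal attendance of 70-80%: composite OR 1.53 to 1.56.
- 60% in the exposed, 80% in the unexposed: 1.07 to 1.10.
- The reverse: 2.17 to 2.18.

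The distortion comes from differential attendance. Non-attendance as such shifts the odds ratio little.

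**The case against.** The strongest defence is that made-and-kept is a deliberate and openly stated outcome. Hypothesis 2 speaks of patients seen by a cardiologist, Aim 2 needs a kept visit to set its time zero, and using one variable for both aims is coherent. Section 5 is concerned with access, and access includes attendance. This stands as a reason to keep the composite, above all for Aim 2. It does not make the composite a measure of referral, and it does not reconcile Sections 4 and 12.1.

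The plan also handles part of the problem. The two times and the missed appointments are measured, and appointment history enters the models, so some attendance-driven association with insurance or race/ethnicity would be adjusted away. How much is unknown, the odds ratios in Step 3 are unadjusted, and no model of factors for either step is specified.

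Four stronger readings are tempting, and the documents do not support them:

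- A reader might infer that the conflict between Sections 4 and 12.1 is what turns referred non-attenders into non-referred patients. It is not: both the Section 4 visit outcome and the 12.1 scoring rule code them no.
- A reader might infer that the Aim 1 results will be materially biased. That needs a large attendance gap remaining after adjustment, and nothing in the documents establishes one.
- A reader might infer that the power statement is wrong. It reproduces. It applies to the scored outcome if 20-25% is the made-and-kept rate, which the text does not say.
- A reader might infer that the intervention will rest on these odds ratios alone. Section 5 assigns its development to the qualitative data, and Section 7.1.2 has Aim 3 supply the framework.

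**Conclusion.** The point holds as two limited findings. The Aim 1 primary outcome has three definitions that classify identifiable patients differently and must be reconciled. The scored version also combines provider referral with patient attendance, and no planned model separates them, so an association labelled as referral may be one with attendance only.

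The size cannot be determined from the documents. Under the assumed rates in Step 3, a factor unrelated to referral gives an odds ratio between 0.92 (a gap of 5 points) and 0.57 (a gap of 30 points), before adjustment. Of the four scenarios, only the 30-point gap goes beyond the effect Aim 1 is powered for. If attendance does not differ by factor, little is lost. The composite is not invalid. The case for acting is that the question is central to Aim 1 and the remedy is cheap.

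**What to change.** Use one definition of the Aim 1 primary outcome in Sections 4 and 12.1, including the opening sentence of 12.1, and state how a visit without a documented referral is scored. Say whether the 20-25% in Section 12.1.1 is the share referred or the share referred and seen. Keep made-and-kept as the Aim 2 exposure.

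For Aim 1, describe composite results as factors associated with completed referral, and report two models beside it:

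- (a) a logistic model of referral made within 6 months, in all patients;
- (b) a model of visit kept within 3 months, among those referred, labelled secondary and with a reduced covariate set.

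The cost is wording plus two regressions on dates the plan already intends to determine. There are real limits. If 20-25% is the share referred, model (b) rests on 0.20 × 1,200 = 240 to 0.25 × 1,500 = 375 patients. At an assumed 80% kept, only 48 to 75 of them would be non-attenders, which is why the covariate set must be small. Model (b) also describes a selected group. Model (a) depends on referral orders being documented in the records, which should be checked in the planned data characterization queries.

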## 5 Background and Significance

Cardiovascular disease among PLWH disproportionately affects URM populations in the U.S., and is an NIH HIV High Priority Topic of research. Multiple cohort studies have found that HIV infection is associated with increased risk of myocardial infarction, ischemic stroke, and heart failure. The literature shows a 27-75% increased risk for CVD attributable to HIV infection. In addition, PLWH are less likely than uninfected persons to receive treatment and procedures related to CVD. Under-represented racial and ethnic populations in the Southeast "HIV-belt" and "Heart Attack belt" face the highest comorbidity from HIV and cardiovascular disease (CVD) in the nation, accounting for 43% of all new HIV infections and CVD death rates 4x greater than other regions. Despite the benefit of cardiology referral for primary prevention of CVD8, URM are the least likely to be referred to cardiologists when overt CVD exists, 10 or when patients are at high risk for CVD. 12,13. Due to historical stigma, PLWH have been reluctant to engage in medical care outside of their HIV provider. Referral

to cardiology care may benefit PLWH at elevated CVD risk, however, we lack knowledge on the determinants of specialty referral and whether referrals improve cardiovascular outcomes for URM PLWH. The field needs knowledge on the effectiveness of cardiology referrals for URM PLWH. Such evidence will ultimately inform clinical care guidelines and health system interventions to improve health for URM populations with HIV.

Thus, the long-term goal of this proposal is to generate evidence-based recommendations for the management of CVD risk in PLWH. The overall objectives of this application are to demonstrate the effect of cardiology referral on CVD outcomes in a racially/ethnically diverse cohort of PLWH, and to generate qualitative data with which to develop of a future intervention. Our central hypothesis is that cardiology referral reduces incident CVD events in URM populations with HIV compared to non-referral. Our hypothesis has been formulated based on our own work identifying that race and provider specialty impact cardiovascular risk management. The rationale for our research is that, once it is known how health disparity populations with HIV access cardiology referrals, and the impact on CVD outcomes, an intervention can be appropriately designed resulting in new and innovative approaches to the management of URM PLWH at elevated CVD risk.

## 6 Study Aims for Aims 1, 2, and 3

Aim 1: To identify factors associated with cardiology referral in under-represented racial and ethnic minority (URM) populations with HIV and elevated cardiovascular risk

Aim 2: To evaluate the association between cardiology referral and CVD outcomes in under-represented racial and ethnic populations with HIV and elevated cardiovascular risk

a. To evaluate the association between cardiology referral and guideline-directed CVD prevention measures in URM populations with HIV and elevated CVD risk

Aim 3: To identify facilitators and barriers to optimal CVD prevention

## 7 Research Design and Methods

## 7.1 Study Design

This study has two overall arms with different study designs and distinct patient populations.

### 7.1.1 Study design for Aims 1 and 2

This study will perform a retrospective electronic health record-driven study of three institutions in the STAR Clinical Research Network.

Aims 1 and 2 will be addressed by a retrospective cohort study design that does not involve enrolling patients. We will analyze patient-level and provider-level data from electronic health records (EHRs) from STAR Clinical Research Network (CRN) institutions that have been mapped to the Common Data Model (CDM). These institutions include Duke University Health System, Vanderbilt University Medical Center, Medical University of South Carolina, and Wake Forest University Health Sciences.

## 7.1.2 Study design for Aim 3

Aim 3 will be addressed by a prospective, qualitative descriptive study enrolling consented participants—patients and health care providers—across four sites to identify the contextual, patient and healthcare provider-reported barriers and facilitators for achieving optimal primary CVD prevention. This aim provides the qualitative framework to develop a contextually appropriate model to prevent CVD among URM PLWH.

## 7.2 Study sites

#### 7.2.1 Study Sites for Aims 1 and 2

Aims 1 and 2: Coordinating Center will collect health system data from Duke University Health System and Vanderbilt University Medical Center, and Medical University of South Carolina, and Wake Forest University Health Sciences via the STAR CRN using CDM.

#### 7.2.2 Study Sites for Aim 3

Aim 3: Duke University Health System, Vanderbilt University Medical Center, Medical University of South Carolina will identify patients and health care providers for interviews; Case Western Reserve University will identify only health care providers for interviews.

Participants will be identified/consented for the qualitative interviews from the following sites:

Duke University Health System (DUHS): Patients & Health Care Providers
 Vanderbilt University Medical Center (VUMC): Patients & Health Care Providers
 Medical University of South Carolina (MUSC): Patients & Health Care Providers

Case Western Reserve University (CWRU): Health Care Providers

## 7.3 Inclusion and exclusion for Aims 1, 2 and 3

#### 7.3.1 Patient EHR data for Inclusion criteria for Aims 1 and 2

- (1) Race equals Black/African-American, American Indian/Alaska Native, Asian, Native Hawaiian/Pacific Islander, or More than one race, and/or Ethnicity equals Hispanic or Latino;
- (2) Documented evidence of HIV positive status (HIV positive diagnosis (ICD10 codes B20-B24, or ICD9 codes 042, V08) and prescription of antiretroviral therapy (ART));
- (3) Documented evidence of elevated AtheroSclerotic CardioVascular Disease risk (ACC/AHA ASCVD 10 year risk ≥5%²⁴, or Framingham Cardiovascular Disease 10 year risk ≥5%²⁵) after HIV diagnosis. The date when the patient first meets either of these CVD risk thresholds and with 1 prior encounter not having CVD risk score defines the **index** time-point for Aim 1 of this study. These risk calculations depend on sex, age, body mass index, diabetes, current smoking, total cholesterol, HDL cholesterol, systolic blood pressure, and treatment for hypertension (defined from diagnosis codes). If cholesterol measures are not available, then body mass index may be used in place of lipids in the Framingham risk calculation; **NOTE: must have at least one prior encounter within 365 days within health system prior to index**
- (4) Presence of a modifiable risk factor: hypertension, diabetes, elevated total cholesterol, elevated LDL cholesterol and/or tobacco use.

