#### 7.3.2 Patient EHR data for Exclusion criteria for Aims 1 and 2:

- (1) Age <18 years of age or >99 years of age at index event;
- (2) Pre-existing ASCVD prior to index event, including a previous diagnosis of any acute myocardial infarction, heart failure, acute coronary syndromes, stable or unstable angina, arterial

revascularization (includes coronary arterial or peripheral), stroke, transient ischemic attack or peripheral arterial disease presumed to be of atherosclerotic origin determined by ICD codes;

- (3) Encounter with cardiology specialist within 1 year prior to index
- (4) Evidence of ART for pre-exposure prophylaxis (i.e., Truvada [emtricitabine/tenofovir disoproxil fumarate] or post-exposure prophylaxis (e.g., Truvada plus raltegravir) without HIV diagnosis.

## 7.4 Inclusion and exclusion criteria for Aim 3

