## 8 Study Procedures

## 8.1 Aims 1 and 2 Study Procedures

We will analyze patient-level and provider-level data from electronic health records (EHRs) from STAR Clinical Research Network (CRN) institutions using CDM. These institutions include Duke University Health System, Vanderbilt Universities, and Medical University of South Carolina.

We (DCRI CC) will retrospectively ask the DataMarts to query the EHR for eligible patients based on age, race, ethnicity, and HIV diagnosis to identify Black/African-American and other URM PLWH. Additional data that are already collected as part of routine medical care will be extracted by sites

from patient EHRs starting at the first clinical contact after January 1, 2010, to create a contemporary cohort with at least 5 years of longitudinal follow-up data. Longitudinal follow- up data will be collected through December 31, 2020. Data will be reviewed and or collected from patient EHR from January 1, 2010 through December 31, 2020. Patients will be included for analysis in this retrospective study at the time of the first clinical encounter during an ("eligibility period") when they meet the inclusion/exclusion criteria (listed below), with a "look back period" of 1 years prior to "enrollment" (i.e., back as far as 2010) to establish medical history and other baseline factors. These dates may be adjusted during the course of the study depending on availability of data in the various DataMarts. The overall scientific premise is depicted in Section 8.2 which shows our approach without specific dates.

DataMarts, Site PIs and Site study teams will link local EHR records with death events and cause of death prior to sending the final dataset to the DCRI CC. Sites will query and link records using National Death Index Plus, State Death records, Social Security Death Mastefile, Hospital death record and/or similar death record for causes of death including cardiovascular death, retaining protected health information needed to query these databases at the site level.

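### The index rule in section 7.3.1(3) asks for a prior encounter without a risk score, not one scored below threshold, so the cohort mixes newly elevated with newly measured risk

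*Combined protocol and SAP*

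**What the plan says.** Section 7.3.1(3) requires a 10-year risk at or above 5% on either the ACC/AHA or the Framingham score, after HIV diagnosis. The index date is the one on which the patient "first meets either of these CVD risk thresholds and with 1 prior encounter not having CVD risk score". Where cholesterol is missing, "body mass index may be used in place of lipids in the Framingham risk calculation". A note adds that the patient "must have at least one prior encounter within 365 days within health system prior to index"; that encounter need not carry a score.

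Three other parts of the plan depend on this date:

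- Section 7.3.2(3) excludes patients with an "Encounter with cardiology specialist within 1 year prior to index".
- Section 12.1 codes the Aim 1 outcome as yes if "a referral is made within 6 months of becoming eligible by CVD risk score" and the appointment is kept within 3 months of referral.
- Section 12.2 sets Aim 2 time zero for a matched pair by the time from Aim 1 baseline to the referred patient's kept appointment.

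Section 8.1 states entry in different terms: "Patients will be included for analysis in this retrospective study at the time of the first clinical encounter during an" eligibility period, once the criteria are met, with a one-year look-back. Extraction starts in January 2010. Section 12.2.1 gives accrual as 2012 to 2016.

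**The concern.** A six-month referral window can be interpreted only if its start means the same thing for every patient. Here the start can be the visit at which risk rose past 5%, or the visit at which someone first recorded enough inputs to compute a score that may have been high for years. In the second case the provider may already have decided about referral, out of view of the outcome window.

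For Aim 1, an association with referral could then partly reflect how long a patient had been at elevated risk, or how complete the record was. For Aim 2, section 12.2 matches within site and baseline year on factors such as age, insurance, risk score and comorbidity. None of these measures time already spent at elevated risk. The sensitivity analyses in section 12.1 (regular attenders, a 12-month window, dropping subgroups with extreme referral rates) do not test this, and section 12.2 carries the same approach into Aim 2.

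The wording also has to be programmed. Section 8.2 describes a study-specific query that applies the criteria at each site, so an ambiguous phrase becomes a choice by whoever writes the code.

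**Working it through.** **The two readings, applied to visit patterns.** L takes the phrase literally (a prior encounter with no score). S takes it as shorthand (a prior encounter with no elevated score).

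- Scored at every encounter, 4.7% then 5.2%. L: not eligible, because no prior encounter is unscored. S: eligible, index at 5.2%. This is the clearest case of onset, and the readings disagree on it.
- Unscored, then below 5%, then at or above 5%. L and S: eligible, index at an observed crossing.
- Unscored at every earlier encounter, then at or above 5%. L and S: eligible, index at first measurement, onset unknown.
- At or above 5%, then unscored, then at or above 5%. The threshold is first met at the first of these encounters. The patient becomes new at the third only if the rule is programmed as the first date on which both conditions hold, or if the earlier elevated score lies outside the extracted record.

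So the readings select different cohorts, and under both the cohort combines observed crossings with first measurements.

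**Entry rule.** A patient who first meets 5% in 2011 has a 2011 index under section 7.3.1(3). Section 8.1, taken with accrual from 2012, can be read as entering that patient in 2012.

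**The plan's own figures (section 12.1.1).** Inputs: 6,000 patients, 20-25% meeting the threshold, 20-25% referred, risk factor prevalence 0.33, two-sided 0.05.

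- Sample size: 6,000 × 0.20 = 1,200; 6,000 × 0.25 = 1,500. Both match.
- Referral rates p0 (unexposed) and p1 (exposed) solve 0.67·p0 + 0.33·p1 = overall rate and [p1/(1−p1)] / [p0/(1−p0)] = OR. Power is then that of a two-proportion test with pooled variance.
- OR 1.6, N = 1,200: at 20% referred, p0 = 0.174, p1 = 0.252, power 88.0%; at 25% referred, p0 = 0.220, p1 = 0.311, power 92.1%. The plan says at least 80%: met.
- OR 1.5, N = 1,500: 85.5% at 20% referred, 90.2% at 25%. The plan says above 85%: met.

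The sample size counts everyone expected to meet the threshold, with no deduction for either reading of the prior-encounter condition.

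**Can the share affected be sized?** Not from the documents. Assume each prior visit is scorable independently with probability p, and k prior visits count. Reading L then drops a share p^k of true new crossers.

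- k = 3: 0.6³ = 22%, 0.9³ = 73%, 0.95³ = 86%.
- k = 12 (3 visits a year for 4 years): 0.6¹² = 0.2%, 0.9¹² = 28%, 0.95¹² = 54%.

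The plan gives neither p nor k, and the 365-day note does not say that the unscored visit must fall in that window. A range of 0.2% to 86% shows only that the quantity is unknown.

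**Power if the analysis is restricted to observed crossers.** With assumed retention from N = 1,200, 20% referred, OR 1.6: 90% retained gives 84.5%; 80% gives 80.2%; 70% gives 75.0%; 50% gives 61.0%. Power stays at 80% down to about 954 patients (954/1,200 = 79.5%) at 20% referred, or 821 (68.4%) at 25%.

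**The case against.** The best defence is that the phrase follows directly on the thresholds, and that section 12.1 speaks of eligibility by risk score when it means meeting the threshold. No qualifying score is therefore a plausible meaning, and under it the always-scored patient is kept. It is also fair that the aims concern people with elevated risk and never call index the onset of it, and that a prevalence-type figure of 20-25% suits a cohort defined by first documented elevation. Both points stand. They do not remove the need to say which reading applies, and the shorthand reading still mixes crossings with first measurements.

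A reader might infer more than the documents support:

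- That index marks a data gap in every patient. It does not: index is still tied to the date a threshold is first met, and some patients will have an observed crossing.
- That 22% to 86% of new crossers are lost. That needs a 365-day window which the rule does not set for the unscored visit, together with unsupported values of p.
- That a patient seen by cardiology 18 months before index, and coded as not referred, is a product of this rule. That comes from the one-year exclusion and would also occur in a true new crosser.
- That long-standing cases fall mostly in the non-referred group. Nothing in the documents shows this.

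**Conclusion.** The point holds as a defect in a stated selection rule. As written, the rule excludes the best-documented new crossers. Under either reading it does not separate newly elevated from newly measured risk. The proportions are unknown, and so are the direction and size of any bias in the Aim 1 odds ratios or the Aim 2 comparisons. No sample size or power statement is wrong because of it. The conclusion rests on the text alone: no section requires a prior score below 5%, and none defines the phrase. It would shrink to a wording matter if nearly all included patients proved to have a computed score below threshold before index, which the extracted data can show.

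**What to change.** - Reword section 7.3.1(3) so that index is the first date either threshold is met, with at least one prior encounter in the look-back at which neither threshold was met. State that an encounter with no computable score satisfies this, how an encounter with only one of the two scores computable is classed, and over what window prior scores are searched, so that a below-threshold score 400 days old is not left unclassified.
- Derive a flag: observed crossing (a computed prior score below both thresholds) or onset unknown (no computable prior score). Report the count in each group.
- Keep both groups in the main analysis. Include the flag as an Aim 1 covariate. Report its balance in the Aim 2 matched cohort, and add it to the matching or propensity score if pairs allow.
- Report the Aim 1 results and the co-primary Aim 2 results in observed crossers as a sensitivity analysis.
- Make the entry rule in section 8.1 refer to this index date, and reconcile it with the 2012 to 2016 accrual period.
- If the query has already been run, state which reading was programmed.

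The cost is one reworded criterion and one variable derived from inputs already being extracted. Because both groups stay in, the flag itself removes no one from the main Aim 1 analysis. The observed-crosser analysis will be smaller, with power as shown above, and matching on the flag may lose some pairs.
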